Appendix 4. Hepatic Monitoring Tests for Treatment-Emergent Abnormality

Selected tests may be obtained in the event of a treatment-emergent hepatic abnormality and may be required in follow-up with subjects in consultation with Lilly or its designee CRP.

Hepatic Monitoring Tests		
Hepatic Hematology ^a	Haptoglobin ^a	
Hemoglobin		
Hematocrit	Hepatic Coagulation ^a	
RBC		
WBC	Prothrombin Time, INR	
Neutrophils		
Lymphocytes	Hepatic Serologies ^{a,b}	
Monocytes	Hepatitis A antibody, total	
Eosinophils	Hepatitis A antibody, IgM	
Basophils	Hepatitis B surface antigen	
Platelets	Hepatitis B surface antibody	
	Hepatitis B Core antibody	
Hepatic Chemistry ^a	Hepatitis C antibody	
Total bilirubin	Hepatitis E antibody, IgG	
Conjugated bilirubin	Hepatitis E antibody, IgM	
Alkaline phosphatase		
ALT	Anti-nuclear antibody ^a	
AST	Alkaline Phosphatase Isoenzymes ^a	
GGT	Anti-smooth muscle antibody (or anti-actin	
Creatinine kinase	antibody) ^a	

Abbreviations: ALT = alanine aminotransferase; AST = aspartate aminotransferase; GGT = gamma-glutamyl transferase; Ig = immunoglobulin; INR = international normalized ratio; RBC = red blood cells; WBC = white blood cells.

a Assayed by Lilly-designated or local laboratory.

^b Reflex/confirmation dependent on regulatory requirements and/or testing availability.

Appendix 5. Blood Sampling Summary

This table summarizes the approximate number of venipunctures and blood volumes for all blood sampling (screening, safety laboratories, immunogenicity, pharmacokinetics, blood glucose, and bioanalytical assays) during the study.

	Blood Volume	Estimated Number	Total
Purpose	per Sample (mL)	of Blood Samples	Volume (mL)
Screening tests (local laboratory) ^a	20	1	20
Clinical laboratory tests (local laboratory) ^a	10	6×2 periods = 12	120
• Study visits (2 periods)			
Pharmacokinetics (central or referral laboratory) ^b	3	14×2 periods (+3)	93
• Study visits (2 periods)		unscheduled) = 31	
Immunogenicity (central or referral laboratory)	10	3×2 periods (+3	90
• Study visits (2 periods)		unscheduled) = 9	
Blood glucose ^a	0.3	6 (+5 discard for	8.4
		cannula patency +3	
		unscheduled) x 2	
		periods = 28	
Pharmacogenetics (stored sample)	10	1	10
Total	341.4		
Total for clinical purposes rounded up to nearest 10	350		

Protocol I8F-MC-GPGS Sampling Summary

a Additional samples may be drawn if needed for safety purposes.

^b Up to 3 additional unscheduled samples may be drawn based on emerging data.

Appendix 6. Classification of Contraceptive Methods

Highly Effective (Less Than 1% Failure Rate) Methods of Contraception:

- Combined oral contraceptive pill and mini pill
- NuvaRing
- Implantable contraceptives
- Injectable contraceptives (such as Depo-Provera[®])
- Intrauterine device (such as Mirena[®] and ParaGard[®])
- Contraceptive patch ONLY women <198 pounds or 90 kg
- Total abstinence or in a same-sex relationship (if this is their preferred and usual lifestyle). Note: periodic abstinence (for example, calendar, ovulation, symptothermal, postovulation methods), declaration of abstinence just for the duration of a trial, and withdrawal are not acceptable methods of contraception
- Vasectomy for men in clinical trials

Effective Methods of Contraception (Must Use Combination of 2 Methods):

- Male condom with spermicide*
- Female condom with spermicide*
- Diaphragm with spermicide
- Cervical sponge
- Cervical cap with spermicide

* The use of male and female condoms as a double-barrier method is not considered acceptable.

Appendix 7. Pancreatic Monitoring

Glucagon-like peptide-1 agonists have been associated with a possible risk of acute pancreatitis. In 2006, the United States prescribing information for exenatide was revised to include the event of pancreatitis. In 2007, the United States prescribing information for this medication was amended to include pancreatitis under "Precautions." Epidemiologic studies have indicated that there is an increased incidence and prevalence of pancreatitis in persons with T2DM.

To enhance understanding of the natural variability of pancreatic enzymes in the T2DM population and, in order to assess for any potential effects of tirzepatide on the exocrine pancreas, amylase and lipase values will be monitored in all current and future clinical trials with tirzepatide.

Additional monitoring will be requested for amylase and/or lipase values $\geq 3 \times ULN$ at any visit, even in asymptomatic subjects (see figure below). Lipase and amylase values may also be obtained at any time during the clinical trials for any subject suspected of having symptoms suggestive of exenatide pancreatitis (such as severe GI signs and/or symptoms), at the investigator's discretion.

Acute pancreatitis is an AE defined as an acute inflammatory process of the pancreas that may also involve peripancreatic tissues and/or remote organ systems. The diagnosis of acute pancreatitis requires 2 of the following 3 features:

- abdominal pain characteristic of acute pancreatitis
- serum amylase and/or lipase $\geq 3 \times ULN$
- characteristic findings of acute pancreatitis on CT scan or magnetic resonance imaging

Most subjects with acute pancreatitis experience abdominal pain that is located generally in the epigastrium, and radiates to the back in approximately one-half of the cases. The pain is often associated with nausea and vomiting. However, experience with GLP-1 agonists has demonstrated that some subjects asymptomatic for classic pancreatitis may demonstrate significant elevations of lipase and/or amylase. For subjects considered by investigators to be asymptomatic for pancreatitis, but whose value(s) for lipase and/or amylase are $\geq 3 \times$ ULN, an algorithm is in place to follow these subjects safely and to quickly reach (or not reach) a diagnosis of pancreatitis.

Pancreatic Enzymes: Safety Monitoring Algorithm for Subjects/Patients without Symptoms of Pancreatitis^{1,2}

Follow this algorithm when the value(s) for serum lipase and/or amylase are ≥ 3X ULN.

1. Symptomatic – related primarily to abdominal pain consistent with pancreatitis; however, severe nausea, vomiting and other symptoms may be considered by the investigator as symptomatic as well.

2. If, at any time, in the opinion of the investigator, patient/subject has symptoms of acute pancreatitis irrespective of L/A results:

- (a) Consult appropriate specialist for assessment and management
- (b) Assess for causes of pancreatitis
- (c) Stop study drug
- (d) Notify Lilly

3. L/A = Lipase and/or amylase. Either or both enzymes can be measured and either or both can be used to meet the algorithm criteria.

4. Abdominal imaging is most valuable when performed at the time of elevated enzyme values. If in the opinion of the radiologist or investigator, it is safe for the patient/subject to receive contrast, an enhanced abdominal CT is preferred. MRI is also an acceptable imaging modality.

5. As minimum, test hepatic analytes, triglycerides, and calcium, and record all concomitant medications

Imaging results positive or negative for signs of acute pancreatitis

Abbreviations: CBC = complete blood count; CT = computed tomography; LFTs = liver function tests; MRI = magnetic resonance imaging. Subjects diagnosed with pancreatitis will be discontinued from the study. Investigators will be responsible for following, through an appropriate healthcare option, these pancreatitis AEs until the events resolve or are explained. Adverse events that meet the diagnostic criteria of acute pancreatitis will be captured as SAEs. For all other pancreatic AEs (such as idiopathic or asymptomatic pancreatic enzyme abnormalities), the investigator will be responsible for determining the seriousness of the event (AE or SAE) and the relatedness of the event to study drug.

Leo Document ID = 27265f5a-b6df-450c-be6b-adf215abc354

Approver: PPD Approval Date & Time: 04-Jun-2019 11:32:58 GMT Signature meaning: Approved

Approver: PPD Approval Date & Time: 04-Jun-2019 15:51:32 GMT Signature meaning: Approved

2. ABBREVIATIONS

Abbreviations pertain to the Statistical Analysis Plan (SAP) only (not the tables, figures and listings [TFLs]).

%AUC(t_{last} - ∞) Percentage of AUC(0- ∞) extrapolated

ADA Anti-drug antibody

AE Adverse event
AI Autoinjector

ALP Alkaline phosphatase

ALT Alanine aminotransferase

AUC Area under the concentration versus time curve

 $AUC(0-\infty)$ Area under the concentration versus time curve from time zero to

infinity

 $AUC(0-t_{last})$ Area under the concentration versus time curve from time zero to

time t, where t is the last timepoint with a measurable concentration

BQL Below the lower limit of quantification

CL/F Apparent total body clearance of drug calculated after extra-vascular

administration

C_{last} Last quantifiable drug concentration

C_{max} Maximum observed drug concentration

CRF Case Report Form

CRU Clinical Research Unit
CSR Clinical Study Report
CV Coefficient of variation

ECG Electrocardiogram

ICH International Conference on Harmonisation

LLOQ Lower limit of quantification

MedDRA Medical Dictionary for Regulatory Activities

MRE Magnetic resonance elastography

PFS Prefilled syringe PG Plasma Glucose

PK Pharmacokinetic(s)

SAP Statistical Analysis Plan

SC Subcutaneous

Final: 08 August 2019 Page 3 of 16

| SD | Standard deviation |
|--------------------|--|
| t _{1/2} | Half-life associated with the terminal rate constant (λ_z) in non-compartmental analysis |
| TBL | Total bilirubin |
| TE | Treatment emergent |
| TFLs | Tables, Figures, and Listings |
| t_{max} | Time of maximum observed drug concentration |
| ULN | Upper limit of normal |
| V _{ss} /F | Apparent volume of distribution at steady state after extravascular administration |
| V _z /F | Apparent volume of distribution during the terminal phase after extra-vascular administration |
| WHO | World Health Organization |

Final: 08 August 2019 Page 4 of 16

3. INTRODUCTION

This SAP has been developed after review of the Clinical Study Protocol (final version dated 4th June 2019).

This SAP describes the planned analysis of the pharmacokinetic (PK), safety and tolerability data from this study. A detailed description of the planned TFLs to be presented in the clinical study report (CSR) is provided in the accompanying TFL shell document.

The intent of this document is to provide guidance for the statistical and PK analyses of data. In general, the analyses are based on information from the protocol, unless they have been modified by agreement with Eli Lilly and Company. A limited amount of information concerning this study (e.g., objectives, study design) is given to help the reader's interpretation. This SAP must be signed off prior to first subject treatment administration for this study. When the SAP and TFL shells are agreed upon and finalized, they will serve as the template for this study's CSR.

This SAP supersedes the statistical considerations identified in the protocol; where considerations are substantially different, they will be so identified. If additional analyses are required to supplement the planned analyses described in this SAP, they may be performed and will be identified in the CSR. Any substantial deviations from this SAP will be agreed upon with Eli Lilly and Company and identified in the CSR. Any minor deviations from the TFLs may not be documented in the CSR.

This SAP is written with consideration of the recommendations outlined in the International Conference on Harmonisation (ICH) E9 Guideline entitled Guidance for Industry: Statistical Principles for Clinical Trials¹ and the ICH E3 Guideline entitled Guidance for Industry: Structure and Content of Clinical Study Reports².

4. STUDY OBJECTIVES

4.1 Primary Objective

To establish comparability between the autoinjector (AI; test) and the prefilled syringe (PFS; reference), as assessed by tirzepatide PK in healthy subjects.

4.2 Secondary Objective

To compare the safety and tolerability of a single subcutaneous (SC) dose of tirzepatide administered by AI (test) versus PFS (reference).

[figure not shown]
5. STUDY DESIGN

This study is a single center, open-label, randomized, 2-period, 2-sequence, crossover study conducted in healthy subjects.

Final: 08 August 2019 Page 5 of 16

CONFIDENTIAL
5-8399714 Sponsor Reference: I8F-MC-GPGS

The study design is as follows:

Abbreviations: AI = autoinjector; CRU = clinical research unit; PFS = prefilled syringe; PK = pharmacokinetics.

Site staff will administer all injections. All injections will be administered in the abdomen whilst the subject is in a sitting or reclining position. Injections will be given in the lower abdominal quadrant. Study injections should be given by a limited number of individuals for consistency.

There will be a washout of at least 35 days between tirzepatide doses. Subjects will be randomized to 1 of the 2 treatment sequences shown above. It is intended that the same number of subjects will be randomized into each treatment sequence.

6. TREATMENT

The following is a list of the study treatment abbreviations that will be used in the TFLs.

| Study Treatment Name | Treatment order in TFL |
|---------------------------|------------------------|
| 5 mg tirzepatide SC (AI) | 1 |
| 5 mg tirzepatide SC (PFS) | 2 |

Final: 08 August 2019 Page 6 of 16

7. SAMPLE SIZE JUSTIFICATION

It is planned that up to approximately 48 subjects may be enrolled so that at least 36 evaluable subjects complete the study.

With 36 subjects, we expect the two one-sided tests for equivalence applied to the lognormal mean ratio to have a power of 98%. This assumes a nominal expected mean ratio of 1.05 (autoinjector over prefilled syringe), a coefficient of variation of 19.6%, and significance level of 0.05 of each one-sided test when testing against an upper limit of 1.25 and lower limit of 0.80. The source of the choice of coefficient of variation is from the final results of study I8F-MC-GPGE.

8. DEFINITION OF ANALYSIS POPULATIONS

The "Safety" population will consist of all enrolled subjects who receive at least one dose of tirzepatide, whether or not they completed all protocol requirements.

The "Pharmacokinetic" population will consist of all subjects who received at least one dose of tirzepatide and have evaluable PK data.

All protocol deviations that occur during the study will be considered for their severity/impact and will be taken into consideration when subjects are assigned to analysis populations.

9. STATISTICAL METHODOLOGY

9.1 General

Data listings will be provided for all data that are databased. Summary statistics and statistical analysis will only be presented for data where detailed in this SAP. For continuous data, summary statistics will include the arithmetic mean, arithmetic standard deviation (SD), median, min, max and N; for log-normal data (e.g. the PK parameters: area under the concentration versus time curve [AUCs] and maximum observed drug concentration [C_{max}]) the geometric mean and geometric coefficient of variation (CV%) will also be presented. For categorical data, frequency count and percentages will be presented. Data listings will be provided for all subjects up to the point of withdrawal, with any subjects excluded from the relevant population highlighted. Summary statistics and statistical analyses will generally only be performed for subjects included in the relevant analysis population. For the calculation of summary statistics and statistical analysis, unrounded data will be used.

Mean change from baseline is the mean of all individual subjects' change from baseline values. Each individual change from baseline will be calculated by subtracting the individual subject's baseline value from the value at the timepoint. The individual subject's change from baseline values will be used to calculate the mean change from baseline using a SAS procedure such as Proc Univariate.

Data analysis will be performed using SAS® Version 9.4 or greater.

Final: 08 August 2019 Page 7 of 16

9.2 Demographics and Subject Disposition

Subject disposition will be listed. The demographic variables age, sex, race, ethnicity, body weight, height and body mass index will be summarized and listed. All other demographic variables will be listed only.

9.3 Pharmacokinetic Assessment

9.3.1 Pharmacokinetic Analysis

Pharmacokinetic parameter estimates will be determined using non-compartmental procedures in validated software program (Phoenix WinNonlin Version 8.1 or later).

Plasma concentrations of tirzepatide (LY3298176) will be used to determine the following PK parameters, when possible:

| Parameter | Units | Definition |
|---------------------------|---------|--|
| AUC(0-t _{last}) | ng.h/mL | area under the concentration versus time curve from time zero to time t, where t is the last timepoint with a measurable concentration |
| $AUC(0-\infty)$ | ng.h/mL | area under the concentration versus time curve from time zero to infinity |
| $%AUC(t_{last}-\infty)$ | % | percentage of $AUC(0-\infty)$ extrapolated |
| C_{max} | ng/mL | maximum observed drug concentration |
| t_{max} | h | time of maximum observed drug concentration |
| t _{1/2} | h | half-life associated with the terminal rate constant (λ_z) in non-compartmental analysis |
| CL/F | L/h | apparent total body clearance of drug calculated after extra-vascular administration |
| V_z/F | L | apparent volume of distribution during the terminal phase after extra-vascular administration |
| V_{ss}/F | L | apparent volume of distribution at steady state after extra-vascular administration |

Additional PK parameters may be calculated, as appropriate.

The software and version used for the final analyses will be specified in the clinical study report. Any exceptions or special handling of data will be clearly documented within the final study report.

Formatting of tables, figures and abbreviations will follow the Eli Lilly Global PK/PD/TS Tool: NON-COMPARTMENTAL PHARMACOKINETIC STYLE GUIDE. The version of the tool effective at the time of PK analysis will be followed.

Final: 08 August 2019 Page 8 of 16

General PK Parameter Rules

• Actual sampling times will be used in the final analyses of individual PK parameters, except for non-bolus pre-dose sampling times which will be set to zero.

- C_{max} and t_{max} will be reported from observed values. If C_{max} occurs at more than one timepoint, t_{max} will be assigned to the first occurrence of C_{max} .
- AUC parameters will be calculated using a combination of the linear and logarithmic trapezoidal methods (linear-log trapezoidal rule). The linear trapezoidal method will be applied up to t_{max} and then the logarithmic trapezoidal method will be used after t_{max}. The minimum requirement for the calculation of AUC will be the inclusion of at least three consecutive concentrations above the lower limit of quantification (LLOQ), with at least one of these concentrations following C_{max}.
- AUC(0-∞) values where the percentage of the total area extrapolated is more than 20% will be flagged. Any AUC(0-∞) value excluded from summary statistics will be noted in the footnote of the summary table.
- Half-life (t_{1/2}) will be calculated, when appropriate, based on the apparent terminal log-linear portion of the concentration-time curve. The start of the terminal elimination phase for each subject will be defined by visual inspection and generally will be the first point at which there is no systematic deviation from the log-linear decline in serum concentrations. Half-life will only be calculated when a reliable estimate for this parameter can be obtained comprising of at least 3 data points. If t_{1/2} is estimated over a time window of less than 2 half-lives, the values will be flagged in the data listings. Any t_{1/2} value excluded from summary statistics will be documented in the footnote of the summary table.
- A uniform weighting scheme will be used in the regression analysis of the terminal loglinear portion of the concentration-time curve.
- The parameters based on the last observed quantifiable drug concentration (C_{last}) will be reported.

Individual PK Parameter Rules

- Only quantifiable concentrations will be used to calculate PK parameters with the exception of special handling of certain concentrations reported below the lower limit of quantification (BQL). Plasma concentrations reported as BQL will be set to a value of zero when all of the following conditions are met:
 - The compound is non-endogenous.
 - The samples are from the initial dose period for a subject or from a subsequent dose period following a suitable wash-out period.

Final: 08 August 2019 Page 9 of 16

- o The timepoints occur before the first quantifiable concentration.
- All other BQL concentrations that do not meet the above criteria will be set to missing.
- Also, where two or more consecutive concentrations are BQL towards the end of a profile, the profile will be deemed to have terminated and therefore any further quantifiable concentrations will be set to missing for the calculation of the PK parameters unless it is considered to be a true characteristic of the profile of the drug.

Individual Concentration vs. Time Profiles

- Individual concentrations will be plotted utilizing actual sampling times.
- The terminal point selections will be indicated on a semi-logarithmic plot.

Average Concentration vs. Time Profiles

- The average concentration profiles will be graphed using scheduled (nominal) sampling times.
- The average concentration profiles will be graphed using arithmetic average concentrations.
- The pre-dose average concentration for single-dose data from non-endogenous compounds will be set to zero. Otherwise, only quantifiable concentrations will be used to calculate average concentrations.
- Concentrations at a sampling time exceeding the sampling time window specified in the protocol, or \pm 10%, will be excluded from the average concentration profiles.
- Concentrations excluded from the mean calculation will be documented in the final study report.
- A concentration average will be plotted for a given sampling time only if 2/3 of the individual data at the timepoint have quantifiable measurements that are within the sampling time window specified in the protocol or ± 10%. An average concentration estimated with less than 2/3 but more than 3 data points may be displayed on the mean concentration plot if determined to be appropriate and will be documented within the final study report.

Treatment of Outliers during Pharmacokinetic Analysis

Application of this procedure to all PK analyses is not a requirement. Rather, this procedure provides justification for exclusion of data when scientifically appropriate. This procedure describes the methodology for identifying an individual value as an outlier for potential exclusion, but does not require that the value be excluded from analysis. The following methodology will not be used to exclude complete profiles from analysis.

Final: 08 August 2019 Page 10 of 16

Data within an Individual Profile

A value within an individual profile may be excluded from analysis if any of the following criteria are met:

- For PK profiles during single dosing of non-endogenous compounds, the concentration in a pre-dose sample is quantifiable.
- For any questionable datum that does not satisfy the above criteria, the profile will be evaluated and results reported with and without the suspected datum.

Data between Individual Profiles

- 1. If n<6, then the dataset is too small to conduct a reliable range test. Data will be analyzed with and without the atypical value, and both sets of results will be reported.
- 2. If n≥6, then an objective outlier test will be used to compare the atypical value to other values included in that calculation:
 - a. Transform all values in the calculation to the logarithmic domain.
 - b. Find the most extreme value from the arithmetic mean of the log transformed values and exclude that value from the dataset.
 - c. Calculate the lower and upper bounds of the range defined by the arithmetic mean $\pm 3*SD$ of the remaining log-transformed values.
 - d. If the extreme value is within the range of arithmetic mean $\pm 3*SD$, then it is not an outlier and will be retained in the dataset.
 - e. If the extreme value is outside the range of arithmetic mean $\pm 3*SD$, then it is an outlier and will be excluded from analysis.

If the remaining dataset contains another atypical datum suspected to be an outlier and $n \ge 6$ following the exclusion, then repeat step 2 above. This evaluation may be repeated as many times as necessary, excluding only one suspected outlier in each iteration, until all data remaining in the dataset fall within the range of arithmetic mean $\pm 3*SD$ of the log-transformed values.

Reporting of Excluded Values

Individual values excluded as outliers will be documented in the final report. Approval of the final report will connote approval of the exclusion.

Final: 08 August 2019 Page 11 of 16

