9.3.2 Pharmacokinetic Statistical Methodology

Two one-sided equivalence tests will be applied to the ratios of each of C_{max} and $AUC(0-\infty)$ using the AI as the test sample and the PFS as the reference. Test limits of the ratios to establish comparability are 0.8 and 1.25.

PK parameters will be evaluated to estimate the relative bioavailability. Log-transformed C_{max} and $AUC(0-\infty)$ will be evaluated in a linear mixed-effects model³ with fixed effects for device, sequence, period, and a random effect for subject within sequence. The treatment differences will be back-transformed to present the ratios of geometric means between AI and PFS treatments and the corresponding 90% CI. Other parameters may be analyzed in this way as needed.

Example SAS code for analysis:

```
proc mixed data=xxx;
    class sequence subject period device;
    model log_pk = sequence period device / ddfm=kr;
    random subject(sequence);
    lsmeans device / pdiff cl alpha=0.1;
    ods output lsmeans=lsmeans diffs=diffs;
run;
```

The t_{max} will be analyzed through non-parametric methods. The median for each treatment and median of differences between the AI and PFS treatments will be presented, along with the approximate 90% CI for the difference. The p-value from a Wilcoxon signed-rank test will also be presented.

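### The SAP's optional mean ± 3 SD outlier deletion is not kept out of the primary equivalence test, and at 36 subjects no all-data result is required, so a few gross autoinjector under-deliveries could be removed.

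*SAP*

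**What the plan says.** SAP 9.3.1, under the treatment of outliers, describes a discretionary procedure: "this procedure provides justification for exclusion of data when scientifically appropriate". It identifies candidate values but "does not require that the value be excluded from analysis". It also carries a limit: "The following methodology will not be used to exclude complete profiles from analysis".

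For data between individual profiles there are two branches.

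- If n<6: "Data will be analyzed with and without the atypical value, and both sets of results will be reported".
- If n≥6: "an objective outlier test will be used to compare the atypical value to other values included in that calculation". The most extreme log value is set aside and compared with the mean ± 3 SD of the rest. If it lies outside, "then it is an outlier and will be excluded from analysis". The step may be repeated while suspected values remain and n≥6.

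On reporting, "Individual values excluded as outliers will be documented in the final report", and approval of the report counts as approval of the exclusion. The same section also has a with-and-without duty for a questionable datum, but it concerns a point inside one profile.

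SAP 9.3.2 defines the primary analysis: "Two one-sided equivalence tests will be applied to the ratios of each of" Cmax and AUC(0-∞), with limits 0.8 and 1.25. It does not mention the outlier procedure. Protocol 10.3 and 10.3.2.2 describe no outlier exclusion, and SAP section 11 declares no change from the protocol's analyses.

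**The concern.** The study asks whether the autoinjector delivers the same exposure as the prefilled syringe. An autoinjector injection that delivers a small fraction of its dose is evidence on that question, and it is also the kind of value a 3 SD rule removes.

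The study is open-label (protocol 5.4 and 7.3), and whether exclusion is scientifically appropriate is judged value by value. With 36 evaluable subjects the n<6 safeguard does not apply, so the plan does not require an all-data test to be shown. Nor does it say which result decides comparability if both are shown.

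Two further readings are open, and the effect depends on them:

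- whether the comparison set is the 36 values of one device or the 72 values of both;
- whether the ban on excluding complete profiles stops both primary values of one injection from being dropped.

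The same data could fail or pass depending on choices made after they are seen.

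**Working it through.** **Inputs from SAP 7 and 9.3.2.** 36 evaluable subjects, planning ratio 1.05, CV 19.6% (read as within-subject), one-sided α 0.05 per test, limits 0.80 and 1.25, stated power 98%. Equal allocation (SAP 5) gives 18 per sequence.

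**The plan's own figure.** σ_w = √ln(1 + 0.196²) = 0.194. SE = 0.194 × √(2/36) = 0.0457, with 34 df. Integrating the two one-sided tests over the residual variance gives 98.2%, so the stated 98% reproduces.

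**Assumptions not in the documents.** Between-subject CV 15, 30 and 40%; Cmax/AUC correlation 0.7; the number of failed autoinjector (AI) injections k and the fraction delivered f, which lowers Cmax and AUC(0-∞) equally.

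**Overall ratio with k failures.** r × f^(k/36), where r is the ratio for the other injections:

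- 0.1^(4/36) = 0.774
- 1.05 × 0.1^(5/36) = 0.763
- 0.1^(6/36) = 0.681
- 0.25^(6/36) = 0.794

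**Simulation.** The n≥6 steps were coded as written and iterated, per device and pooled. The test used period-adjusted within-subject differences from complete pairs. There were 2,000 trials per cell (Monte Carlo SE at most 1.1 points). The table gives the share of trials in which both endpoints pass, with ranges over the three between-subject CVs. All four overall ratios lie outside the limits.

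| AI failures of 36 | Delivered | r | Overall ratio | All data | Rule per device | Rule pooled |
|---|---|---|---|---|---|---|
| 4 | 10% | 1.00 | 0.774 | 0% | 76-99% | 95-99% |
| 5 | 10% | 1.05 | 0.763 | 0% | 26-38% | 91-95% |
| 6 | 10% | 1.00 | 0.681 | 0% | 2-3% | 91-99% |
| 6 | 25% | 1.00 | 0.794 | 0% | 0.5-4% | 13-98.5% |

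In the last row the pooled figure is 98.5%, 50% and 13% at between-subject CV 15, 30 and 40%. With correlation 0.5 or 0.9 the first two rows hardly move: 0%, 76-99%, 96-99%; and 0%, 24-44%, 91-95%.

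**Why per-device screening weakens at five failures (masking).** Take k equal failures, each lowered by d on the log scale. Setting one aside leaves a share p = (k−1)/35 of failures among the rest. Its distance from their mean is d(1−p), and their SD is at least d√(p(1−p)).

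- k=4: p = 0.086, so 0.914d against 3 × 0.280d = 0.840d. Removal is possible if d is large.
- k=5: p = 0.114, so 0.886d against 3 × 0.318d = 0.954d. Removal is not possible.

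Random variation softens this: at CV 15% the average number of failed Cmax values removed was 4.0 of 4, 3.1 of 5 and 0.4 of 6.

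**Overall ratio inside the limits.** Here deletion only reverses a failure caused by inflated variance.

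- r = 1.0, with 1, 2 or 3 failures at 10% (0.938, 0.880, 0.825): 61-62%, 2-3% and 0-0.1% pass with all data; 94-99.7% after the rule.
- r = 1.05, all data versus per device: one failure 88-89% versus 96-97%; two 18-19% versus 95-96%; three 0.1-0.2% versus 92-95%.
- r = 1.05, four failures (0.813): 0% versus 75-96% after the rule.

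**Where little changes.** Three of 36 at 50% delivery: 89-90% versus 92-97%. Twelve of 36 at 50%: under 1% throughout. Clean-data type I error per endpoint at 0.80 or 1.25 (5,000 trials): 4.7-5.7% with all data, 5.0-5.9% per device, 5.3-6.6% pooled.

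**Protective reading of the complete-profile ban.** If an injection that loses its Cmax must keep its AUC(0-∞), the pass rate after the rule is 0% in the first three table rows and at most 0.6% in the fourth.

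**The case against.** The strongest reply is the complete-profile ban. An injection at 10% of dose is aberrant throughout. Both endpoints must pass, so rescuing the conclusion means dropping that injection's Cmax and its AUC(0-∞), which is close to excluding the profile. Read that way, the reversal all but disappears. This stands as a reading, but the SAP does not say that the ban covers derived values, and the test acts on individual values.

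Second, the rule sits in 9.3.1, while the inferential model in 9.3.2 has no exclusion step, and the protocol bases the PK analyses on all dosed subjects with evaluable data. That supports a reading in which the primary test is untouched. It does not settle the matter, because the exclusion is from analysis without qualification.

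Third, deletion is optional, and deleting a real device failure would be hard to call scientifically appropriate. Exclusions are documented, databased data are listed (SAP 9.1) and device complaints are listed (protocol 10.3.1.1), so a reader could rerun the test. All true: the percentages describe the rule if applied and are not the chance of a wrong conclusion. But visibility does not fix in advance which result governs.

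Fourth, the cases with a ratio outside the limits need 4 to 6 of 36 staff-given injections (11-17%) to fail grossly, and the documents give no failure rate. At the planning ratio a single failure changes little. Both points limit the concern; two or more failures at 10% delivery still change the result.

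Last, the simulation used complete pairs, whereas the SAP's mixed model would keep the unpaired syringe value. The effect of that difference was not tested.

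**Conclusion.** The concern holds as a gap in pre-specification that can decide the primary conclusion; it is not evidence of an error in the result. The deletion is optional, nothing keeps it out of the primary test, and no all-data test is required at n=36.

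Its size depends on the reading. Applied to both endpoints and not blocked by the complete-profile ban, it can turn a 0% pass rate into 76-99% with four gross failures and an overall ratio of 0.774. With the ban read as protective, the reversal does not occur. The figures rest on assumed failure counts, delivered fractions, between-subject CV and endpoint correlation, and on a complete-pair analysis. The concern is confined to gross failures. It should be fixed; confidence is medium, because the effect depends on readings that the SAP leaves open.

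**What to change.** Add to SAP 9.3.2:

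> The primary two one-sided tests for Cmax and AUC(0-∞) use all evaluable values in the Pharmacokinetic population; the between-profile mean ± 3 SD test in 9.3.1 removes no value from them. If that test flags values, the tests without those values are reported beside them as a labelled sensitivity analysis, and the all-data result governs the comparability conclusion.

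In 9.3.1, state whether the screen is run per device or pooled. The exclusion step can stay for descriptive summaries and secondary parameters, and the pre-dose rule and the AUC and half-life reliability rules are unaffected. With this wording, the reach of the complete-profile ban no longer matters for the primary test.

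The cost is two sentences, one clause, and one extra run only if values are flagged. The drawback is that a genuinely aberrant value stays in the primary analysis and may widen the 90% CI.
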